4.11.3 Clinical Laboratory Evaluation

Hematology, serum chemistry, coagulation, thyroid function test, and urinalysis tests are listed in table 6.

Table 6 Clinical Laboratory Tests

Chemistry	Hematology
Alanine aminotransferase (ALT)/ serum glutamate pyruvic transaminase (SGPT)	Red blood cell (RBC); Erythrocyte
Albumin	Hemoglobin
Alkaline phosphatase (ALP)	Hematocrit
Aspartate aminotransferase (AST); serum glutamic oxaloacetic transaminase (SGOT)	White blood cell (WBC); Leukocytes
Bicarbonate	Neutrophils (Absolute)
Blood urea nitrogen (BUN)	Neutrophils band form (Absolute)
Calcium	Lymphocytes (Absolute)
Chloride	Monocytes (Absolute)
Creatinine	Eosinophils (Absolute)
Direct bilirubin	Basophils (Absolute)
Glucose	Neutrophils/Leukocytes (%)
Indirect bilirubin	Neutrophils band form/Leukocytes (%)
Lactate dehydrogenase (LDH)	Lymphocytes/Leukocytes (%)
Magnesium	Monocytes/Leukocytes (%)

Phosphate Potassium Protein Sodium Total bilirubin (TBL) Urate (Uric Acid) Urea	Eosinophils/Leukocytes (%) Basophils/Leukocytes (%) Platelets
Coagulation	Urinalysis
Activated partial thromboplastin time (aPTT) International normalized ratio (INR) Prothrombin time (PT)	pH Specific Gravity Bilirubin Glucose Ketones Leukocyte esterase Nitrite Occult blood Protein Urobilinogen
Thyroid function test	
Thyroid stimulating hormone (TSH) Thyroxine, free (Free T4) Triiodothyronine (Total T3) Triiodothyronine, free (Free T3)	

Absolute value, change from baseline, and percentage change from baseline for continuous parameters (analytes) of hematology, serum chemistry, coagulation, and thyroid function tests will be summarized by visit and DLs/arm in each phase using descriptive statistics (mean, median, STD, minimum, maximum, and number of subjects).

Baseline and post-baseline hematology, serum chemistry, and coagulation tests will be classified as Grade 0, Grade 1, Grade 2, Grade 3, and Grade 4 based on CTCAE v5.0. Shift of these tests from baseline CTCAE grade to the worst postbaseline CTCAE grade will be presented by DLs/arm in each phase using the number and percentage of subjects at each shift category. If applicable, some laboratory tests have two CTCAE grade directions: hypo and hyper, where both directions will be presented in the shift table.

Proteinuria determined by dipstick shift from baseline to worst postbaseline will be provided if applicable. Thyroid function tests shift from baseline to worst postbaseline will be provided using normal, abnormal (not clinically significant) and abnormal (clinically significant)

The liver function tests (ASL, ALT, ALP, and TBL) will be summarized in the following worst postbaseline categories:

- AST3 x upper limit of normal (ULN)
 - 3 x upper limit of normal (ULN)
 - 5 x ULN
 - 10 x ULN
 - 20 x ULN
- ALT
 - 3 x ULN
 - 5 x ULN
 - 10 x ULN

Confidential

- 20 x ULN
- AST or ALT
 - 3 x ULN
 - 5 x ULN
 - 10 x ULN
 - 20 x ULN
- TBL
 - 1.5 x ULN
 - 2 x ULN
- ALP
 - < 2 ULN
- (AST or ALT) and TBL
 - AST or ALT \geq 3 x ULN and TBL \geq 2 x ULN
- (AST or ALT) and ALP and TBL
 - AST or ALT \geq 3 x ULN and ALP < 2 x ULN and TBL \geq 2 x ULN

Subjects meet below conditions will be listed if data is applicable:

- ALT or AST \geq 3 x ULN
- TBL \geq 2 x ULN
- ALP < 2 x ULN

All the laboratory values and CTCAE grades (if applicable) will be presented in data listings.

All laboratory tests will be presented in data listings.

Pregnancy test will be presented in data listing.

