### 11.4. Adverse Events of Special Interest in NT-I7

The following AEs are of special interest in subjects receiving NT-I7, as defined below and must be reported by the investigator expeditiously to the Sponsor and/or Sponsor's Safety designee irrespective of regulatory seriousness criteria and the relatedness to NT-I7.

Immune-related adverse event (irAE) is defined as an AE associated with drug exposure that is consistent with an immune-mediated mechanism of action when there is no clear alternate etiology. For events which are potentially immune-related, additional information such as serologic, immunologic, and histologic (biopsy) data and use of steroids or immunosuppressants will be used to support an irAE diagnosis.

- Potential drug-induced liver injury that includes an elevated ALT or AST  $\geq 3 \times$  ULN in combination with an elevated bilirubin  $\geq 2 \times$  ULN and, at the same time, an alkaline phosphatase (ALP)  $< 2 \times$  ULN; no other reason can be found to explain the combination of increased AST or ALT, and TBL, such as viral hepatitis A, B, or C; preexisting or acute liver disease; or another drug capable of causing the observed injury. (86)
- Conditions (regardless of grade) suggestive of an autoimmune disorder or immune-related adverse events (irAEs), including but not limited to hepatitis, pneumonitis, colitis, pancreatitis, endocrinopathies (including but not limited to thyroiditis, Type 1 diabetes mellitus, adrenal insufficiency), myocarditis, myositis/polymyositis, rheumatoid arthritis, vasculitis, neuritis, systemic lupus erythematosus, Sjogren's syndrome, multiple sclerosis, Guillain-Barre syndrome and myasthenia gravis
- Symptoms and signs suggestive of hypersensitivity, cytokine release, or infusion reaction syndromes with a different underlying pharmacological etiology
- Grade  $\geq 2$  diarrhea
- Grade  $\geq 2$  AST/ALT and Grade  $\geq 2$  total bilirubin elevation with constitutional symptoms
- Grade  $\geq 3$  hypoxia or dyspnea
- Grade  $\geq 2$  pleural effusion that is not due to the underlying disease (e.g., non-malignant pleural effusion)

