### 11.6. Events of Clinical Interest (ECI) in Pembrolizumab

Selected adverse events are also known as Events of Clinical Interest (ECI) and must be reported to the Sponsor within 24 hours.

Events of clinical interest in pembrolizumab studies include:

1. An overdose of pembrolizumab, as defined in Section 11.7—Treatment of Overdose, that is not associated with clinical symptoms or abnormal laboratory results.

2. An elevated AST or ALT lab value that is greater than or equal to 3X the upper limit of normal and an elevated total bilirubin lab value that is greater than or equal to 2X the upper limit of normal and, at the same time, an alkaline phosphatase lab value that is less than 2X the upper limit of normal, as determined by way of protocol-specified laboratory testing or unscheduled laboratory testing.\*

*\*Note: These criteria are based upon available regulatory guidance documents. The purpose of the criteria is to specify a threshold of abnormal hepatic tests that may require an additional evaluation for an underlying etiology. The study site guidance for assessment and follow up of these criteria can be made available. It may also be appropriate to conduct additional evaluation for an underlying etiology in the setting of abnormalities of liver blood tests including AST, ALT, bilirubin, and alkaline phosphatase that do not meet the criteria noted above. In these cases, the decision to proceed with additional evaluation will be made through consultation between the study investigators and the Sponsor. However, abnormalities of liver blood tests that do not meet the criteria noted above are not ECIs for this study.*

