4.11 Safety Analysis

Safety analysis will be summarized by Phase 2 arms and by dose group for dose Phase 1b based on safety analysis set unless otherwise specified.

For safety shift tables, schedule and unscheduled measurements up to 30 days after last dose date will be included in worst postbaseline results derivation.

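### SAP 4.11.3 sets no timing rule for its combined liver-test rows; read literally, they can pair values from different visits, while the protocol requires them at the same time

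*SAP*

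**What the plan says.** SAP 4.11.3 states that AST, ALT, ALP and total bilirubin (TBL) "will be summarized in the following worst postbaseline categories". The rows under that line are of two kinds. Most concern one analyte or the transaminases alone, including an ALP row for values below 2 × ULN. Two are combinations:

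- AST or ALT ≥ 3 × ULN and TBL ≥ 2 × ULN
- AST or ALT ≥ 3 × ULN and ALP < 2 × ULN and TBL ≥ 2 × ULN

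Neither combination has a same-visit, same-sample or time-window condition, and the SAP does not say in which direction ALP is worst. A listing follows, introduced by "Subjects meet below conditions will be listed if data is applicable". Its three conditions (ALT or AST ≥ 3 ×, TBL ≥ 2 ×, ALP < 2 × ULN) are separate bullets with no connecting word and no timing.

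SAP 4.11 says, for shift tables, that scheduled and unscheduled values up to 30 days after the last dose "will be included in worst postbaseline results derivation". Nothing further defines worst for the liver table.

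The protocol ties the analytes together in time. Section 11.4 (NT-I7 AESI) takes ALT or AST ≥ 3 × ULN in combination with bilirubin ≥ 2 × ULN, adds the condition "at the same time, an alkaline phosphatase (ALP", with ALP below 2 × ULN, and requires that no other cause be found. Section 11.6 (pembrolizumab ECI) uses the same cut-offs and requires "at the same time, an alkaline phosphatase lab value that is less than 2X the upper limit of normal".

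SAP Section 6, on changes from the protocol, does not mention a difference on this point.

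**The concern.** A worst post-baseline value works for a single analyte. It does not work for a criterion that needs two values high and a third low in the same blood sample. If each analyte is first reduced to its own extreme, the link between them is lost: the worst ALT may come from week 3, the worst bilirubin from month 6 and the worst ALP from the last visit.

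The three-analyte row is the table entry a reader would consult for biochemical potential liver injury. The DLT reported in Phase 1b at 1,200 µg/kg was a Grade 3 ALT increase, so the liver table will be read closely. A row that uses the protocol's cut-offs without its timing could include subjects who never met the criterion and omit subjects who did.

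**Working it through.** The plan gives no figure to reproduce, so the check is one of logic. The cut-offs come from SAP 4.11.3 and protocol 11.4 and 11.6. The laboratory values in the table below are illustrative assumptions.

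**Rules.** At each post-baseline draw t let A = 1 if AST or ALT ≥ 3 × ULN, B = 1 if TBL ≥ 2 × ULN, and C = 1 if ALP ≥ 2 × ULN (which disqualifies).

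- Same draw (protocol timing): some t has A = 1, B = 1, C = 0.
- Worst values, highest ALP: max A = 1, max B = 1, max C = 0.
- Worst values, lowest ALP: max A = 1, max B = 1, min C = 0.
- Two-analyte row: same draw needs A = B = 1 at one t; worst values need max A = 1 and max B = 1.

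**Illustrative subjects** (ALT or AST / TBL / ALP, in × ULN, successive draws), three-analyte row:

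| Subject | Draws | Same draw | Highest ALP | Lowest ALP |
|---|---|---|---|---|
| 1 | 1/0.8/1.2; 5/3/1.5; 1.5/1/2.6 | counted | not counted | counted |
| 2 | 4/0.8/1.2; 1/0.9/1.4; 1.2/2.5/1.8 | not counted | counted | counted |
| 3 | 1/0.8/1.2; 5/3/2.6 | not counted | not counted | counted |

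In the two-analyte row, subjects 1 and 3 are counted under both rules. Subject 2 is counted only under the worst-value rule.

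**All two-draw patterns.** Each draw has 2 × 2 × 2 = 8 states, so two draws give 8 × 8 = 64 patterns.

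- Patterns with at least one true same-draw case: 64 − 7 × 7 = 15.
- (A, B) patterns over two draws: 16. Those with A at least once and B at least once: 16 − 4 − 4 + 1 = 9. Those with A and B together in at least one draw: 16 − 3 × 3 = 7.

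*Three-analyte row, highest ALP.* ALP must stay below 2 × at both draws (1 of 4 ALP patterns), so 9 × 1 = 9 are counted and 7 of them are true. Invented: 9 − 7 = 2. Missed: 15 − 7 = 8.

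*Three-analyte row, lowest ALP.* ALP must be below 2 × at one draw or more (3 of 4), so 9 × 3 = 27 are counted, including all 15 true patterns. Invented: 27 − 15 = 12. Missed: 0.

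*Two-analyte row.* Counted: 9 × 4 = 36. True: 7 × 4 = 28. Invented: 36 − 28 = 8. Missed: 0, since any concurrent pair also satisfies the worst-value rule.

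The patterns are not equally likely, so these counts show which errors can occur, not how often. Neither ALP direction reproduces the protocol timing. Draws can be far apart: 35 cycles × 21 days = 735 days of treatment.

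**The case against.** The strongest reply is that the SAP never spells out the per-subject derivation. Each combined row is written as one joint condition, and a programmer could evaluate it at each visit and count anyone who ever meets it. That is fair: combining values across visits is an inference from the heading. But nothing in the SAP requires the by-visit reading, and the heading points the other way.

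Three stronger readings are tempting, and the documents do not support them.

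- *A reader might infer that protocol-defined events would be lost or invented.* SAP 4.11.2 defines AESI and ECI by reference to protocol 11.4 and 11.6 and tabulates and lists them separately. The laboratory rows do not feed those counts.
- *A reader might infer that any disagreement between the laboratory row and the AESI count would show the error.* The two can differ even with perfect timing. The liver AESI also requires that no other cause be found, which a laboratory row cannot show, and overall AESI and ECI counts include other kinds of event.
- *A reader might call the error likely, or size it at 4 points in an arm of 25.* The entry limits (ALP up to 2.5 × ULN, or 5 × with liver involvement or bone metastases) make ALP above 2 × plausible. However, a subject whose ALP stays there fails both the same-draw and highest-ALP rules, so is not misclassified between them. Also, 25 is the evaluable efficacy target, whereas safety tables use all treated subjects.

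There are safeguards too. A concurrent case missed by the three-analyte row still appears in the two-analyte row, and all laboratory values are listed, so cases can be recovered by hand. The dedicated liver listing helps less as written: with its bullets taken separately, the ALP condition would list anyone with a normal ALP.

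**Conclusion.** Wrong as written. Under the literal heading, the two-analyte row can over-count non-concurrent elevations and cannot miss a concurrent pair. The three-analyte row can over-count under either ALP direction, and misses true concurrent cases only if worst ALP means the highest value.

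The conclusion assumes that the heading governs the combined rows, as its placement implies. If the programming already works by sample date, the results are right and only the text needs correcting.

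The effect is confined to a descriptive laboratory summary and its listing. No hypothesis test, stopping rule or dose decision is attached to these rows. The frequency of misclassification cannot be derived from the documents. For scale only, one subject is 1/30 = 3.3 percentage points in an arm with the maximum 30 enrolled and treated, and 1/6 = 16.7 points in a six-subject Phase 1b dose level.

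**What to change.** Add one sentence to SAP 4.11.3: for the two combination rows and the matching listing, a subject is counted if all conditions are met at any one post-baseline sample date (or within a short window that the SAP states). Join the three listing conditions with the word and. Keep worst post-baseline values for the single-analyte rows only, and state there which direction is worst for ALP. If a non-concurrent version of the combined rows is also wanted, show it separately under its own label.

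The cost is one SAP sentence and minor programming. No new data are needed.

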	
d. Total bilirubin <math>\leq 1.5 \times</math> institutional upper limit of normal (ULN) OR direct bilirubin <math>\leq</math> ULN for subjects with total bilirubin levels <math>> 1.5 \times</math> ULN
 
e. AST(SGOT)/ALT(SGPT) <math>\leq 2.5 \times</math> ULN (AST and/or ALT <math>\leq 5 \times</math> ULN for subjects with liver metastasis)
 
f. Alkaline phosphatase <math>\leq 2.5 \times</math> ULN (<math>\leq 5 \times</math> ULN for subjects with documented liver involvement or bone metastases)
 
g. Creatinine <math>\leq 1.5 \times</math> ULN or Creatinine clearance (CrCl) <math>\geq 30</math> mL/min for subject with creatinine levels <math>> 1.5 \times</math> ULN. CrCl should be calculated per institutional standard
 
h. INR and aPTT <math>\leq 1.5 \times</math> ULN unless the subject is receiving anticoagulant therapy as long as PT or aPTT is within therapeutic range of intended use of anticoagulants.
 
9. ECG demonstrating Fridericia's corrected QT interval (QTcF) <math>< 470</math> ms. Patients with QTcF <math>\geq 470</math> ms will require clearance by a local cardiologist.
 
10. Female subjects who are either postmenopausal for at least 1 year, are surgically sterile for at least 6 weeks; female subjects of childbearing potential must agree to remain abstinent (refrain from heterosexual intercourse) or to use dual methods of contraception for the duration of study treatment and for 120 days after the last dose of study treatment (pembrolizumab and/or NT-I7). Female subjects of childbearing potential (including women who have had a tubal ligation) must have a negative serum or urine pregnancy test within 72 hours prior to Cycle 1, Day 1. If the urine test is positive, or cannot be confirmed as negative, a serum pregnancy test will be required.
 
11. Non-sterile male subjects who are sexually active with female partners of childbearing potential must agree to remain abstinent (refrain from heterosexual intercourse) or to use highly effective method(s) of contraception for the duration of study treatment and for 120 days after the last dose of study treatment (pembrolizumab and/or NT-I7).
 
12. And meet the requirements for the intended stages and arms (disease specific inclusion criteria), as following:
 
Applicable to the Dose escalation phase (Phase 1b) only:
 
a. Relapsed/refractory advanced solid tumors  Note: Prior anti-PD-1/anti-PD-L1 requires a 4-week washout period.
 
b. Willing to provide pre- and on-treatment biopsies
 
Applicable to the Dose expansion phase (Phase 2a) only:
 
Anti-PD-1/anti-PD-L1 refractory criteria for CPI-treated TNBC, NSCLC, and SCLC

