##### 4.1. Inclusion Criteria

Subjects must meet all the following criteria for study entry:

1. Must be  $\geq 18$  years on the day of signing informed consent.
2. Be willing and able to provide written informed consent/assent for the study.
3. Subjects with histologically or cytologically confirmed advanced or metastatic solid tumors who have disease progression after treatment with all available therapies for metastatic disease that are known to confer clinical benefit, or are intolerant to treatment, or refuse standard treatment.
4. Have measurable disease per RECIST 1.1 as assessed by the enrolling physician. Lesions situated in a previously irradiated area are considered measurable if progression has been demonstrated in such lesions.
5. Subjects enrolling in the Phase 1b and Arms I, IV, IVa, V, and Va of the Phase 2a, and the Biomarker Cohort must have biopsiable disease (i.e., have at least 1 tumor lesion that is accessible and feasible for biopsy) as determined by the enrolling physician. Willing to provide archival tumor tissue sample or newly obtained core or excisional biopsy of a tumor lesion not previously irradiated. Formalin-fixed, paraffin embedded (FFPE) tissue block is preferred to slide. Newly obtained biopsy is preferred to archived tissue.
6. Eastern Cooperative Oncology Group (ECOG) performance status 0-1
7. Subjects must have a life expectancy of greater than or equal to 12 weeks per assessment from the enrolling physician.
8. Subjects must have adequate organ function as defined below:
  - a. Absolute neutrophil count  $\geq 1,500/\mu\text{L}$
  - b. Platelets  $\geq 100,000/\mu\text{L}$
  - c. Hemoglobin  $\geq 9.0 \text{ g/dL}$  or  $\geq 5.6 \text{ mmol/L}$  (Criteria must be met without erythropoietin dependency and without packed red blood cell transfusion within last 2 weeks)
  - d. Total bilirubin  $\leq 1.5 \times$  institutional upper limit of normal (ULN) OR direct bilirubin  $\leq \text{ULN}$  for subjects with total bilirubin levels  $>1.5 \times \text{ULN}$
  - e. AST(SGOT)/ALT(SGPT)  $\leq 2.5 \times \text{ULN}$  (AST and/or ALT  $\leq 5 \times \text{ULN}$  for subjects with liver metastasis)
  - f. Alkaline phosphatase  $\leq 2.5 \times \text{ULN}$  ( $\leq 5 \times \text{ULN}$  for subjects with documented liver involvement or bone metastases)

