2.2 Definition of Baseline

Baseline value is defined as the last available value collected before the first dose of study drugs unless otherwise specified. If assessment time is collected, time should be compared as well.

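### The liver-threshold rows in SAP 4.11.3 ignore baseline, so some subjects whom the protocol admits with raised values can be counted without any change

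*SAP*

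**What the plan says.** SAP 4.11.3 states that the liver tests "will be summarized in the following worst postbaseline categories". AST, ALT, and AST or ALT are cut at 3, 5, 10 and 20 x ULN, and total bilirubin (TBL) at 1.5 and 2 x ULN. Two combined rows follow: AST or ALT at least 3 x ULN with TBL at least 2 x ULN, and the same with ALP below 2 x ULN. None of these rows refers to baseline, and neither does the accompanying listing of subjects who meet the limits.

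Protocol 4.1 (repeated in the Synopsis) sets the entry limits:

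- Criterion 8e: AST/ALT up to 2.5 x ULN in general, and up to 5 x ULN "for subjects with liver metastasis".
- Criterion 8d: total bilirubin up to 1.5 x "institutional upper limit of normal (ULN) OR direct bilirubin" within ULN where the total exceeds 1.5 x ULN. This second route has no stated upper limit on total bilirubin.

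Baseline is already defined in SAP 2.2: "Baseline value is defined as the last available value collected before the first dose of study drugs unless otherwise specified". SAP 4.11.3 also uses it in another display of the same tests: "Shift of these tests from baseline CTCAE grade to the worst postbaseline CTCAE grade will be presented by DLs/arm in each phase".

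**The concern.** The entry limits overlap the table's cut-offs. A subject who starts above a cut-off and stays there is counted alongside one who rose from normal, and the table does not separate them.

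This matters more than usual here for three reasons. The trial has no control arm, so there is no concurrent background rate to set the counts against. Protocol 5.1 reports one DLT at 1200 µg/kg, a Grade 3 ALT increase. Potential drug-induced liver injury is an AESI for NT-I7 (Protocol 11.4), and the same laboratory limits define an event of clinical interest for pembrolizumab (Protocol 11.6). Readers will look at these rows and may take them as treatment-emergent.

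Elsewhere the SAP does condition on baseline: QTcF has change-from-baseline categories (4.11.5), TEAEs must start or worsen on or after first treatment (4.11.2), and ADA is split into treatment-emergent and boosted (4.13). The ULN-multiple liver rows are an exception.

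**Working it through.** The plan gives no figure of its own to reproduce.

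**Step 1. Row limits against entry limits, for a subject whose post-baseline values equal baseline.**

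| Row | Can it be met with no change? |
|---|---|
| AST/ALT 3 x ULN | Yes with liver metastasis (entry to 5 x); no otherwise (entry to 2.5 x) |
| AST/ALT 5 x ULN | Only at exactly 5 x, with liver metastasis |
| AST/ALT 10 x, 20 x ULN | No |
| TBL 1.5 x ULN | Through the direct-bilirubin exception; at the ordinary limit only if the row includes exactly 1.5 x |
| TBL 2 x ULN | Only through the direct-bilirubin exception |
| Combined rows | Only with both liver metastasis and the direct-bilirubin exception |

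Example: a subject with liver metastasis enters at ALT 3.5 x, TBL 2.2 x with direct bilirubin within ULN, and ALP 1.5 x. The subject is eligible on these tests and meets both combined rows before the first dose.

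The single-test rows show no comparison sign in the text available to me. That may be lost in conversion, so I draw nothing from it.

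**Step 2. Illustrative size for the 3 x AST-or-ALT row, subjects with liver metastasis, no drug effect.** All inputs are assumptions:

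- true AST and ALT log-normal, log-SD 0.6, correlation 0.7;
- median 1.2 x ULN in the central case, range 0.9-1.6;
- screened at 5 x ULN or below;
- within-subject log-SD 0.15 with 3 post-baseline draws (low noise), or 0.25 with 6 draws (high noise).

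With B the event of being at or above 3 x at baseline and C the event that the worst later value is at or above 3 x:

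P(C) = P(B and C) + P(not B) x P(C given not B)

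- Low noise: P(B) = 9.4% and P(B and C) = 8.3%. The rest is 90.6% x 5.8% = 5.3%. Total 8.3 + 5.3 = 13.6%.
- High noise: P(B) = 10.8% and P(B and C) = 9.7%. The rest is 89.2% x 15.1% = 13.5%. Total 9.7 + 13.5 = 23.2%.

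So 14-23% meet the row and 9-11% are at or above 3 x at baseline. The baseline part is 8.3/13.6 = 61% of the count with low noise and 9.7/23.2 = 42% with high noise. Over medians 0.9-1.6, the row runs from about 6% to 38% and the baseline share from about 4% to 20%.

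**Step 3. What a baseline condition leaves.** Among subjects below 3 x at baseline, the rate is P(C given not B): 5.8% (low noise) to 15.1% (high noise), still with no drug effect. This is the effect of taking a maximum over several draws.

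**Step 4. Scale in one arm.** Let q be the share of an arm already at or above a limit. The documents give no value. Expected count = nq; chance of at least one = 1 - (1 - q)^n. For n = 30 and q = 2%, 5%, 10%, 15%:

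- expected 0.6, 1.5, 3.0, 4.5 subjects;
- chance of at least one 45%, 79%, 96%, 99%.

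I have no basis for a frequency for the combined rows and give none.

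**The case against.** The case for leaving the table alone is fair on several counts.

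- **Baseline context exists.** SAP 4.11.3 has CTCAE grade shifts, change from baseline by visit and full laboratory listings, and SAP 4.4 summarises liver metastasis at baseline. This stands for single analytes. The shifts do not use these ULN cut-offs and do not cover the combined rows, for which a reader must go to the listings.
- **The combined row is a screen.** With ALP, it matches the event-of-clinical-interest limits in Protocol 11.6, which also carry no baseline condition. The AESI in Protocol 11.4 excludes cases with another explanation, such as pre-existing liver disease, and SAP 4.11.2 tabulates AESIs separately. This stands, and is a reason to keep the present counts.
- **Nothing depends on the table.** No stopping rule, test or planned between-arm comparison uses it. DLTs have their own criteria, and Phase 1b dose selection is complete. This stands and sets the priority.
- **A baseline condition does not remove noise.** Correct, as Step 3 shows.

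Two stronger readings are tempting. A reader might infer that the plan labels unchanged subjects as liver toxicity. It does not: the rows are described only as worst post-baseline categories. A reader might also infer that differences between arms in these rows would merely reflect how many subjects have liver metastasis. The documents give no prevalence by arm. Nor is the contrast with other subjects necessarily sharp: with a median of 0.8-0.9 x ULN and log-SD 0.6, about 0.8-5.4% of subjects without liver metastasis would also cross 3 x by noise.

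**Conclusion.** The point holds in a limited form. The rows take no account of baseline, and the protocol's entry limits reach into some of them. For AST/ALT this concerns the 3 x row in subjects with liver metastasis. For bilirubin and the combined rows it arises mainly through the direct-bilirubin exception.

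Under the assumptions in Step 2, baseline elevation accounts for roughly two fifths to three fifths of a 14-23% no-effect count in subjects with liver metastasis. Visit-to-visit variation accounts for the rest. These percentages depend on assumed distributions. The overlap between entry limits and row limits does not.

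The existing shift tables reduce the problem for single tests and leave it open for the combined rows. Priority is low: this is a worthwhile improvement to a descriptive safety table.

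**What to change.** In SAP 4.11.3:

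1. Keep the current any-post-baseline counts.
2. Beside them, for each threshold and each combined row, give the count among subjects who did not meet that row at baseline, with those subjects as the denominator.
3. Show subjects who already met the row at baseline on a separate line, with the worst value as a multiple of baseline.
4. Add a baseline-status flag to the listing of subjects who meet the liver limits.
5. Note under the table that the baseline-conditioned counts still include crossings due to variation between visits.

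The cost is a few lines of SAP text and some table programming. The baseline values are already collected and defined in SAP 2.2, and no safety information is lost. The downside is a longer table with smaller denominators.
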